5.6.2. Analysis Methods

Analysis of the other secondary efficacy endpoints will follow the same approach as in the analysis of the primary efficacy endpoint analysis. These analyses will be based on the ‘Up-to-Day 180’ observation period for the ITT population with censoring as defined above (Section 2.6).

In addition to be above endpoints, the key secondary endpoints (time to symptomatic VTE events or VTE-related deaths, all-cause mortality) will also be analyzed based on the ‘Up-to-Day 180’ observation period for the ITT population.

The cumulative distribution function of the time to first occurrence of each of these endpoints will be estimated by the Kaplan-Meier method and tested using a log-rank test, stratified by tumor type. In addition, a Cox proportional hazard model with treatment and stratification factor as covariates will be fitted. A point estimate along with 2-sided 95% CI for the treatment effect of RRR (RRR=100 x [1-HR] %) will be provided.

The cumulative event rate derived from Kaplan-Meier estimate will also be displayed graphically to evaluate the timing of event occurrence and the consistency of the treatment effect over time. No multiplicity adjustment will be performed for the analysis of these endpoints.

Frequency summary (N, %) of the total number of deaths and the primary cause of death, total number of subjects with myocardial infarction (MI), stroke, and other arterial thrombosis (ATE) events will also be presented for the Up-to-Day 180 observation period.

5.7. End-of-Study Vital Status Summary

In this study, vital status data (alive/dead) was collected at the Day 210 follow up visit for all randomized subjects, except for those who had died during the double-blind period. The Cochran-Mantel-Haenszel (CMH) test, adjusting for the stratification factor (APC/non-APC), for the association between the treatment group and each of these endpoints will be performed provided there are non-zero entries in each cell of the 2x2 treatment-by-endpoint table.

6. SAFETY

6.1. Bleeding

The primary safety objective of this study is to assess the major bleeding events as defined by International Society on Thrombosis and Haemostasis (ISTH) based on the CEC classification from the time of first dose to two days after the last dose of study drug.

6.1.1. Bleeding Events Classification

Like efficacy outcomes, the same independent CEC will adjudicate and classify bleeding events per the definitions in the CEC Charter.

Bleeding events will be classified as major, clinically relevant non-major, or minor bleeding using the ISTH classification as follows:

Major Bleeding

Major bleeding is defined as clinically overt bleeding that is associated with:

- A reduction in hemoglobin of 2 g/dL or more, or
- A transfusion of 2 or more units of packed red blood cells or whole blood, or
- Occurrence at a critical site defined as intracranial, intra-spinal, intraocular, pericardial, intra-articular, intra-muscular with compartment syndrome, retroperitoneal, or
- Fatal outcome

Clinically Relevant Non-Major Bleeding

Clinically relevant non-major bleeding defined as overt bleeding not meeting the criteria for major bleeding but associated with:

- Medical intervention
- Unscheduled contact (visit or telephone call) with a physician
- Temporary cessation of study treatment, or
- Discomfort such as pain, or impairment of activities of daily life

Minor Bleeding

All other overt bleeding episodes not meeting the criteria for major or clinically relevant non-major bleeding will be classified as minor bleeding (corresponds to minimal bleeding event captured on the case record form).

Imputation Rules for Partial Bleeding Start Dates

If the bleeding start date is a partial date (only unknown day)

- If only the day is missing, and the month and year are known, the month and year of the AE will be compared with the month and year of double-blind medication start date.
 - If the both the month and year of the bleeding event is equal to the month and year of double-blind medication start date, then the imputed day will be the start day of medication.
 - If the month or the year of the bleeding event is different, then the imputed day will be the 1st day of the month.

6.1.2. Primary Safety Endpoint of Bleeding

The primary safety endpoint is ISTH major bleeding as adjudicated by the CEC.

6.1.2.1. Definition

The primary safety endpoint is defined as the time from the first study drug to first occurrence of ISTH major bleeding events in Section 6.1.1 during the ‘**On-Treatment**’ observation period (observation periods defined in Section 2.6).

Censoring - subjects who do not experience endpoint events during the ‘**On-Treatment**’ observation period will be censored at the minimum of (last dose date + 2, death date).

6.1.2.2. Analysis Methods

The primary safety endpoint will be analyzed using the same approach as in the primary efficacy endpoint but based on the ‘**On-Treatment**’ observation period for the Safety population (randomized and taken at least one dose of the study drug) with censoring as defined above.

The cumulative distribution function of the time to first occurrence of the primary safety endpoint will be estimated by the Kaplan-Meier method and tested using a log-rank test, stratified by tumor type.

The estimate of the hazard ratio (HR), RRR (RRR=100*[1-HR] %) and the 95% confidence intervals for the treatment effect will be provided based on a stratified Cox proportional hazard model (stratification factor: APC or non-APC) and including treatment group as a binary covariate (i.e., rivaroxaban, placebo).

Incidence of major bleeding events and primary location of bleeding will also be summarized for each treatment group.

The primary safety endpoint will also be summarized for the subgroups defined in Section 2.7.

6.1.3. Supportive Analysis of the Primary Safety Endpoint of Bleeding

In addition to the primary safety analysis for major bleeding safety endpoint, supportive analysis will be performed to account for multiple major bleeding event times experienced by the same subject. Multiple major bleeding events will be analyzed using the recurrent event analysis by Anderson-Gill (1982)¹¹ method. The supportive analyses will be performed for the ISTH major bleeding endpoint and the clinically relevant non-major bleeding endpoint and will be based on the ‘On-Treatment’ observation period for the safety analysis population. All tests will be performed with the use of SAS version 9.4 or higher (SAS® Institute).

6.1.4. Secondary Safety Endpoints of Bleeding

6.1.4.1. Definition

Secondary safety endpoints of bleeding include time to:

- Clinically relevant non-major bleeding
- Minor bleeding (corresponds to minimal bleeding)
- Any bleeding event (defined as a composite of ISTH major, clinically relevant non-major and minor bleeding)

6.1.4.2. Analysis Methods

The secondary safety endpoints of bleeding will be analyzed using the same approach as in the primary safety endpoint. The analysis will be based on the Safety population in the ‘On-Treatment’ observation period with censoring as defined above (Section 2.6).

Each of the secondary endpoints will be tested using a log-rank test, stratified by tumor type (APC or non-APC). In addition, a Cox proportional hazard model with treatment and stratification factor as covariates will be fitted. A point estimate for hazard ratio (rivaroxaban/placebo) along with 2-sided 95% CI for the treatment effect of RRR (RRR=100 x [1-HR] %) will be provided.

The cumulative event rate derived from Kaplan-Meier estimate will also be displayed graphically to evaluate the timing of event occurrence and the consistency of the treatment effect over time.

Summary of Safety Endpoints Analysis Methods			
Endpoint	Observation Period	Analysis Population	Method
Primary Endpoint ISTH Major bleeding event			
Secondary Endpoints 1. Clinically relevant non-major bleeding 2. Minor bleeding 3. Composite bleeding event (major, clinically non-major and minor) (CEC Adjudicated Events)	On-Treatment	Safety	Kaplan-Meier Estimates (Cumulative event rates and log-rank test) Cox-model (HR, 95% CI)

6.2. Adverse Events

The original terms used in the CRFs by investigators to identify AE will be coded using the Medical Dictionary for Regulatory Activities (MedDRA) version 20.0 or higher.

A treatment-emergent adverse event (TEAE) is defined as any adverse event that starts between the first study medication administration and the last study medication administration + 2 days.

Only the AEs with start dates between the first dose date and the last dose date+2 days will be included in all TEAE summaries, including study (double-blind period) withdrawal and treatment discontinuation.

As per the protocol (Section 12.4), in this study suspected outcome events are excluded from AE/SAE collection and reporting, regardless of seriousness or severity. These suspected events will be captured on the eCRF as outcome events and will be waived from SAE collection and unblinding and exempted from expedited reporting. These events include: symptomatic lower extremity proximal DVT, asymptomatic lower extremity proximal DVT, symptomatic lower extremity distal DVT, symptomatic upper extremity DVT, symptomatic non-fatal PE, incidental PE, VTE-related death, all-cause mortality, ATE events (e.g., MI, stroke), visceral VTE, and all bleeding events.

The number (%) of subjects who had treatment-emergent adverse events will be summarized by System Organ Class (SOC) and preferred term (PT) for the Safety analysis population.

The number and percentage of subjects experiencing TEAEs will be summarized by treatment group for the Safety analysis population, and stratification factor: APC or non-APC.

In addition, overall summaries of **all AEs** (all AEs that are reported from start of study through the Day 210/End-of-Study) for the safety population will also be presented. Summary table of AE by body system and preferred term will also be presented for all AEs.

Adverse events will also be summarized by treatment group, severity, relationship to study medication, combined severity and relationship to study medication, action taken during treatment, and subject outcome. They will also be presented by treatment group, SOC, and PT.

Differences in the percentages of AEs between the two groups will be summarized and the 95% CI for the difference using the normal approximation to binomial distribution will be provided.

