In this study with a six-month planned treatment with rivaroxaban, the primary efficacy outcome variable is a composite of any symptomatic DVT, proximal asymptomatic DVT, any PE, and VTE-related death. The study design allows fixed treatment duration of 6 months on each successfully randomized subject. Assuming a cumulative incidence rate of 14.5% for the primary composite events in the placebo group and 6.0% cumulative incidence rate in the rivaroxaban treatment group, a total sample of about 700 randomized subjects (350 per treatment group) will be required to demonstrate approximately 60% relative risk reduction (RRR) in the primary efficacy composite endpoint with a 2-sided Type 1 error rate of 5% and >90% statistical power (calculation performed by EAST 6.3 software) assuming a 20% discontinuation rate. Towards the end of the enrollment phase, approximately 800 subjects were planned to be randomized into the study due to the high subject discontinuation rate. In addition, this sample size will allow for 80% statistical power in each stratum (APC or non-APC) for slightly larger differences in incidence rates between the two randomized treatment groups to be statistically significant.

Essentially, the above overall sample size estimate is calculated based on the following assumptions:

- Effect size: absolute difference in event rates = 8.5%, RRR = 58.6%
 - Primary efficacy composite endpoint event rate in the placebo arm: 14.5%
 - Primary efficacy composite endpoint event rate in the rivaroxaban arm: 6%
- Power: >90%
- Overall α level: 5%, 2-sided
- Probability of dropping out of the study: 20%
- Duration of enrollment period: 12 months
- Duration of study: 6 months (fixed for each randomized subject)

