5. EFFICACY

5.1. Analysis Specifications

5.1.1. Level of Significance

All statistical tests will be 2-sided and conducted at 5% significance level unless specified otherwise.

The fixed-sequence step down procedure with a priori ordered hypotheses will be used to control the type I error for multiple testing (Section 5.5). If the result of a test in the sequence is not significant, the tests in lower hierarchical order will be interpreted as not significant regardless of the actual p-value. All confidence intervals will be estimated at the 95% level.

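### The normal-approximation 95% interval for adverse-event percentage differences has no sparse-count alternative: it has zero width at 0 vs 0 and can under-cover when one arm's rate is near zero

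*SAP*

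**What the plan says.** SAP section 6.2 has treatment-emergent adverse events tabulated by system organ class and preferred term in the Safety population. For the between-group difference in percentages, "the 95% CI for the difference using the normal approximation to binomial distribution will be provided". It names no variance form, continuity correction or sparse-count method. Section 5.1.1 fixes the level: "All confidence intervals will be estimated at the 95% level".

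Three other provisions limit the reach of that sentence:

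- Section 6.2 keeps suspected outcome events (VTE, death, arterial events, visceral VTE and all bleeding) out of adverse-event collection.
- Sections 6.1.2.2 and 6.1.4.2 analyse major and other bleeding by Kaplan-Meier, stratified log-rank and Cox methods.
- Section 6.2.4 pre-lists three groups of events of special interest (severe hypersensitivity, severe skin reactions, severe liver injury). It says only that they are summarised and names no interval, so the general sentence in 6.2 is the only one that could apply to them.

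**The concern.** The normal approximation for a difference of proportions estimates its variance from the observed proportions. With no events that variance is zero, and with one or two events it is small and poorly estimated. The interval can then be too short on the side that matters for safety, the upper limit of the excess on active treatment. It can also exclude zero on a handful of events. At stake is whether intervals labelled 95% in the rare-event rows behave as such.

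**Working it through.** **Inputs.** Level 95% (section 5.1.1). Arm sizes come from section 1.4: "a total sample of about 700 randomized subjects (350 per treatment group) will be required", later "approximately 800 subjects were planned to be randomized into the study due to the high subject discontinuation rate", which is 400 per arm at 1:1. The size of the Safety population is not stated, so both 350 and 400 are used. True adverse-event rates are assumed.

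**The plan's own figures.** The only figure attached to the interval is its nominal 95%. The sample size behind n does reproduce. With 350 × 0.8 = 280 evaluable per arm and 14.5% vs 6.0%, the mean rate is 0.1025 and z = (0.085·√280 − 1.96·√(2·0.1025·0.8975)) / √(0.145·0.855 + 0.06·0.94) = (1.422 − 0.841)/0.425 = 1.37. Power is about 91.5%, in line with the stated >90%.

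**Formulas.** With a and b the observed proportions:

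- Wald: (a − b) ± 1.96·√(a(1−a)/n + b(1−b)/n).
- Newcombe: with Wilson limits (l₁, u₁) for a and (l₂, u₂) for b, lower = (a − b) − √((a − l₁)² + (u₂ − b)²) and upper = (a − b) + √((u₁ − a)² + (b − l₂)²).

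**0 vs 0.** Wald: 0 ± 0. Newcombe: ±1.09% (n = 350) or ±0.95% (n = 400).

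**4 vs 0, n = 350.** a = 4/350 = 1.143%.

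- Wald: standard error √(0.01143·0.98857/350) = 0.568%, so 1.143% ± 1.114% = 0.03% to 2.26%.
- Newcombe: Wilson limits are 0.445% to 2.901% for a, and 0 to 1.086% for b. Lower = 1.143 − √(0.698² + 1.086²) = −0.15%; upper = 2.90%.
- Fisher's exact p = 0.12.

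At n = 400 the intervals are 0.02% to 1.98% (Wald) and −0.13% to 2.54% (Newcombe).

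**Coverage.** The two binomials are enumerated exactly. The conditional columns drop the 0 vs 0 table, because a preferred term that nobody reported has no row.

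| True rates | Wald, all tables, 350 / 400 | Wald, ≥1 event, 350 / 400 |
|---|---|---|
| 0.25% vs 0% | 58% / 63% | >99.9% / 99.9% |
| 0.5% vs 0% | 82% / 86% | 99.7% / 99.9% |
| 1% vs 0% | 86% / 91% | 89% / 92% |
| 2% vs 0% | 92% / 90% | 92% / 90% |
| 0.5% vs 0.25% | 89% / 86% | 95% / 90% |
| 1% vs 0.25% | 94% / 90% | 95% / 90% |
| 1% vs 0.5% | 94% / 95% | 95% / 95% |
| 5% vs 2% | 95% / 95% | 95% / 95% |
| 0.25% vs 0.25% | 99% / 99% | 99% / 98% |
| 1% vs 1% | 95.4% / 95.4% | 95.4% / 95.4% |

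**Hand check, 1% vs 0%, n = 400.** With 1 vs 0 events the Wald upper limit is 0.74%, below the true 1%; with 2 vs 0 it is 1.19%. So the only upper-side miss, given an event, is exactly one event: 400·0.01·0.99³⁹⁹/(1 − 0.99⁴⁰⁰) = 0.0725/0.982 = 7.4%. Lower-side misses add 0.3%, giving 92.3% coverage. The same step at n = 350 gives 10.8% and 0.3%, so 88.9%.

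Newcombe's coverage was at least 95.0% in every scenario tried.

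**The case against.** The case for leaving the text alone is strong on scope.

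- **Key harms.** A reader might infer that the trial's most important harms carry faulty intervals. The SAP does not support this: bleeding, thrombotic events and deaths are not in these tables, and bleeding has time-to-event analyses.
- **The lowest figures.** A reader might take 58% to 86% coverage (0.25% or 0.5% vs 0%) as typical of printed rows. Those shortfalls come almost wholly from 0 vs 0 tables: at n = 400 such tables have probability 36.7% and 13.5%, and coverage given any event is 99.9%. They matter only for rows printed whatever the count, as the pre-listed special-interest groups might be.
- **Rare events in general.** Under-coverage is not general: with equal rare rates the interval over-covers. The 1% vs 0.25% shortfall is present at 400 per arm but nearly absent at 350.
- **Rarity.** Nothing shows that the special-interest groups are all rare. The liver group includes raised transaminases and bilirubin in patients on systemic cancer therapy.
- **Reading.** The SAP does not say Wald. A continuity correction of 1/n would give ±0.29% (n = 350) or ±0.25% (n = 400) at 0 vs 0, and mostly higher coverage. The separate Data Presentation Specifications might settle the form.
- **Use.** No test, margin or stopping rule depends on these intervals, and counts appear beside them.

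All of this stands, and it makes the point small. It does not remove the zero-width interval under the usual reading, the 89% to 92% coverage for 1% or 2% vs 0% given an event, or the exclusion of zero at 4 vs 0.

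**Conclusion.** The point holds as a minor one. The SAP fixes a single interval method for adverse-event differences without a sparse-count alternative. In its usual unpooled form that method has zero width at 0 vs 0, and covers roughly 89% to 92%, given at least one event, when one arm's rate is zero and the other's is 1% to 2%. Most misses are on the upper side. For commoner events (2% vs 1% and above) coverage is 94.8% to 95.0% in the cases reported.

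This rests on assumed event rates, 350 to 400 per arm, the unpooled form without continuity correction and, for the special-interest groups, on the general sentence in section 6.2 applying to them. The efficacy conclusions and the bleeding analyses are unaffected.

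**What to change.** In SAP section 6.2, replace the normal-approximation interval for adverse-event percentage differences with a named score-type interval, Newcombe or Miettinen-Nurminen. State whether it also applies to the special-interest groups in section 6.2.4, and how a 0 vs 0 row is shown. This is one option in the analysis program. The only downside is wider intervals for rare events; those for common events change little.

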6.2.1. Imputation Rules for Missing AE Dates

A conservative approach will be used to handle the missing dates for adverse events. The rules for handling the incomplete AE onset dates will be as follows:

- If only the day is missing, and the month and year are known, the month and year of the AE will be compared with the month and year of double-blind medication start date.
 - If the both the month and year of the AE is equal to the month and year of double-blind medication start date, then the imputed day will be the start day of medication.
 - If the month or the year of the AE are different, then the imputed day will be the 1st day of the month.
- If only the month is missing, and day and year are known, the year of the AE will be compared with the year of the double-blind medication start date.
 - If the year of the AE is equal to the year of the double-blind medication start date, then the imputed month will be the same as the month of the double-blind medication.
 - If the year is different, then the month will be as January.
- If both the day and month are missing but year is known, compare the year with the year of the double-blind medication start date.
 - If the year is the same, then impute the AE start date as the same as the first dose date.
 - If the year is different, then impute the AE start date to be January 1.
- If the day, month and year are all missing, then the imputed date for the AE will be the date of the first dose of study medication.

After imputation if the AE start date is greater than the AE end date, then the AE start date will be set equal to the AE end date.

- No imputation will be done for AE end date.

6.2.2. Adverse Events Resulting in Withdrawal from the Study and Discontinuation of Treatment:

The number and percentage of subjects who withdrew from the double-blind period due to an **TEAE** (TEAE led to withdrawal from the study) will be summarized by treatment group and listed by subject. In addition, **TEAEs** that led to discontinuation of study drug (drug withdrawal) will also be summarized by treatment group.

In addition, overall summaries of **all AEs** (all AEs that are reported from start of study through the Day 210/End-of-Study) with action taken of drug withdrawal will also be presented

6.2.3. **Serious Adverse Events (SAE) and Deaths during the Study:**

The number and percentage of serious TEAE and deaths will be summarized by treatment group and listed by subject.

Serious TEAE that led to study drug discontinuation will be summarized by treatment group and listed by subject.

In addition, **all serious AEs** and deaths (all AEs that are reported from start of study through the Day 210/End-of-Study) will also be summarized.

6.2.4. **Adverse Events of Special Interest**

In addition to the overall AEs summaries, certain AEs that are considered to be Adverse Events of Special Interest (AESI) will be summarized. The special interest TEAEs for the following groups will be summarized:

- Suspected severe hypersensitivity reaction
 - SMQ preferred terms included are: anaphylaxis, angioedema, severe urticaria, bronchospasm, idiopathic urticaria, anaphylactic reaction, anaphylactic shock, anaphylactoid reaction, and anaphylactic shock.
- Severe skin reactions
 - SMQ preferred terms included are: Stevens-Johnson Syndrome.
- Suspected severe liver injury
 - SMQ preferred terms included are: drug-induced liver injury, acute hepatic failure, hepatic failure, hepatocellular injury, liver injury, mixed liver injury, alanine aminotransferase abnormal, alanine aminotransferase increase, aspartate aminotransferase abnormal, aspartate aminotransferase increased, blood bilirubin increased, blood bilirubin unconjugated increased, hyperbilirubinaemia, and liver function test abnormal.

Summaries of the special interest TEAEs will be based on the safety population.

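### SAP 6.2.1: the missing-month rule can date an on-treatment adverse event before the first dose and so remove it from every TEAE summary, contrary to the section's stated conservative approach

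*SAP*

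**What the plan says.** SAP Section 6.2.1 opens with its intent: "A conservative approach will be used to handle the missing dates for adverse events". It then covers four patterns of incomplete onset date.

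- **Month missing.** "If only the month is missing, and day and year are known, the year of the AE will be compared with the year" of the first dose. In the same year, "then the imputed month will be the same as the month of the double-blind medication". Otherwise, "If the year is different, then the month will be as January".
- **Day missing.** If month and year are those of the first dose, the first-dose day is used. Otherwise the first of the month is used.
- **Day and month missing.** "If the year is the same, then impute the AE start date as the same as the first dose date". Otherwise 1 January is used.
- **Everything missing.** The first-dose date is used.

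A final check follows: "After imputation if the AE start date is greater than the AE end date, then the AE start date will be set equal to the" end date.

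Section 6.2 defines a TEAE as "any adverse event that starts between the first study medication administration and the last study medication administration + 2 days" and admits only AEs dated in that window to the TEAE summaries. Sections 6.2.2 to 6.2.4 build the withdrawal, discontinuation, serious-TEAE and special-interest summaries on the same definition. Sections 6.2 to 6.2.3 also plan summaries of all AEs, of all AEs with drug withdrawal as the action taken, and of all serious AEs and deaths, through Day 210/End-of-Study.

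Section 6.1.1 has its own rule for bleeds with an unknown start day. If month and year match the first dose, "then the imputed day will be the start day of medication". No end-date check follows it.

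**The concern.** For a safety table, a conservative date rule counts an AE as treatment-emergent unless the record shows otherwise. The other three patterns in 6.2.1 do this: where the known part of the date is compatible with the first-dose day, the onset is set to the first dose. The same-year month-missing branch does not. It keeps a known day of month, attaches the first-dose month, and accepts whatever date results. If the AE day is earlier in the month than the first-dose day, the imputed onset is before treatment.

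What is at stake is the classification of such AEs in the main safety tables, including serious ones and those that led to stopping study drug. The record is just as compatible with an onset in a later month, on treatment.

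The bleeding rule has a smaller gap in the other direction. A bleed that began and ended earlier in the first-dose month is given a start on the first-dose day, which falls in the On-Treatment window of the primary safety endpoint (Section 6.1.2.1).

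**Working it through.** The SAP gives no figure on this point, so there is none to reproduce. The check has three parts.

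**1. Mechanism.** Take a first dose on 20 March and an AE with day 5, month unknown, same year.

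- The rule gives 5 March, which is 15 days before the first dose, so the AE is not a TEAE.
- Under 180 days of treatment (20 March to 15 September), six dates fit the record and are on treatment: the 5th of April, May, June, July, August and September.
- The end-date check cannot restore the AE. It acts only when the start is later than the end, and then moves the start earlier.

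**2. Size.** Inputs from the SAP are the rule in 6.2.1, the TEAE window in 6.2 and the 180-day treatment period in 1.2. Assumptions not in the SAP are that every calendar date is equally likely as first-dose date (three calendar years enumerated) and that true onset is uniform over days 0 to 181 after the first dose. For each pair of dates the month was deleted, the rule applied, and imputed dates before the first dose counted.

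- Share of on-treatment AEs in the first-dose year: 0.752.
- Share of those dated before the first dose: 0.452.
- AEs in the following year get January of that year, which is always after the first dose: share misdated 0.
- All missing-month on-treatment AEs: 0.752 × 0.452 + 0.248 × 0 = 0.340.

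| Assumed onset | Same-year branch | All missing-month AEs |
|---|---|---|
| Uniform, days 0–181 | 45% | 34% |
| Within first 90 days | 45% | 40% |
| Within first 60 days | 45% | 42% |
| Within first 30 days | 45% | 43% |
| Weighted to early onset (exponential, scale 45 days) | 40% | 36% |

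As a cross-check, with AE day and first-dose day independent and uniform on 1 to 30, P(AE day < first-dose day) = (30 × 29 / 2) / 900 = 435/900 = 48%. This is the same-year branch only.

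The same-year share depends strongly on the first-dose day: 0% for day 1, 27% for day 10, 43% for day 15, 59% for day 20 and 94% for day 30. With uniform onset, a further 1% or so of same-year cases yield a date that does not exist, such as day 31 in a 30-day month. The rule does not say what to do then.

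**3. The proposed rule.** It picks the earliest date on or after the first dose that matches the recorded day and year. If the true onset is on treatment, that date cannot be later than the true onset, so it lies within the TEAE window. The share of true on-treatment AEs misdated as pre-dose is therefore 0% by construction. Because the imputed start is no later than the true one, the end-date check is not triggered for these AEs when the end date is correct.

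**The case against.** The strongest reply is that this matters little in practice.

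- A known day and year with an unknown month is an unusual pattern, and the SAP gives no count. This stands: few records are likely to be affected.
- The affected AEs are not lost from reporting, because they appear in the all-AE, all-AE drug-withdrawal and all-serious-AE summaries. This stands. It is only partial cover, since the special-interest summaries and the summary of withdrawal from the double-blind period are specified for TEAEs only.
- AE comparisons are descriptive, and VTE, arterial events, deaths and bleeds are excluded from AE collection (Section 6.2). The month rule therefore touches no primary or key secondary endpoint. This stands.

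A reader might infer that about half of all missing-month AEs are misdated. The documents do not support that. The 48% figure describes the same-year branch under independent uniform days. The January branch misdates no AE from a later year, so the overall share is about a third, up to 43% if onsets are early.

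A reader might also infer that each affected AE is certainly misclassified. It is not. The early date is certain, but AEs are summarised from the start of the study and there is a two-week screening period, so some of these AEs may truly be pre-dose.

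On bleeding, a reader might infer that the primary safety endpoint is distorted, or that the conservative label is broken there too. Neither follows. That label is stated for AEs only, the gap adds an on-treatment bleed rather than losing one, and the SAP does not say that a bleeding end date is collected. What remains is that 6.1.1 lacks a check that 6.2.1 has. Since bleeds are excluded from AE collection, the check in 6.2.1 does not plainly extend to them.

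**Conclusion.** The same-year month-missing branch of 6.2.1 is wrong as written, because it defeats the section's own stated intent. Under uniform onset and evenly spread first-dose dates, about 45% of true on-treatment AEs in that branch (40% to 48% over the assumptions tried) are dated before the first dose and drop out of every TEAE-based summary. Across all on-treatment AEs with only the month missing, the share is about 34% (up to 43% with early onset). These are shares of what is probably a very small number of records, so the effect on the tables is likely to be small. The reason to act is that the rule is clearly faulty, cheap to correct, and awkward to change once treatment assignment is known. The bleeding gap is secondary and conditional on an end date being recorded.

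**What to change.** In 6.2.1, replace the same-year month-missing branch with:

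1. If the AE day is on or after the first-dose day and the first-dose month contains that day, use the first-dose month.
2. Otherwise, use the next month that contains that day.
3. If that month falls outside the recorded year, treat the AE as pre-dose.
4. Then apply the existing end-date check.

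This is better than simply taking the later of the imputed date and the first-dose date. With a first dose in December and an earlier AE day in the same year, the AE can only be pre-dose. A plain floor would count it as treatment-emergent, while step 3 classifies it correctly. Step 2 also settles the non-existent dates.

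In 6.1.1, add: where a bleeding end date is recorded and the imputed start is later than it, set the start to the end date. A bleed that ended before the first dose is then not counted as On-Treatment.

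The cost is a few lines of SAP text and of derivation code, with no new data. The change should be made before unblinding.
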